#### 6.2.4 FDA Guidelines for Adverse Event Reporting

All adverse events meeting the definition of serious, unexpected and associated to the research intervention will be reported to the IRB according to their guidelines found on the IRB's website and the IND file according to the following guidelines and FDA definition of events:

Associated with the use of the drug: There is a reasonable possibility that the experience may have been caused by the drug.

Disability: A substantial disruption of a person's ability to conduct normal life functions.

Lifethreatening adverse drug experience: Any adverse drug experience that places the patient or subject, in the view of the investigator, at immediate risk of death from the reaction as it occurred, i.e., it does not include a reaction that, had it occurred in a more severe form, might have caused death.

Serious adverse drug experience: Any adverse drug experience occurring at any dose that results in any of the following outcomes: death, a life threatening adverse drug experience, inpatient hospitalization or prolongation of existing hospitalization, a persistent or significant disability/ incapacity, or a congenital anomaly/birth defect. Important medical events that may not result in death, be life threatening, or require hospitalization may be considered a serious adverse drug experience when, based upon appropriate medical judgment, they may jeopardize the patient or subject and may require medical or surgical intervention to prevent one of the outcomes listed in this definition.

Unexpected adverse drug experience: Any adverse drug experience, the specificity or severity of which is not consistent with the current investigator brochure; or, if an investigator brochure is not required or available, the specificity or severity of which is not consistent with the risk information described in the general investigational plan or elsewhere in the current application, as amended. "Unexpected," as used in this definition, refers to an adverse drug experience that has not been previously observed (e.g., included in the investigator brochure) rather than from the perspective of such experience not being anticipated from the pharmacological properties of the pharmaceutical product.

#### 6.2.5 IND Safety Reports

The sponsor shall notify FDA and all participating investigators in a written IND safety report of:

Any adverse experience associated with the use of the drug that is both serious and unexpected.

Any finding from tests in laboratory animals that suggests a significant risk for human subjects including reports of mutagenicity, teratogenicity, or carcinogenicity.

Each notification shall be made as soon as possible and in no event later than 15 calendar days after the investigators initial receipt of the information.

Telephone and facsimile transmission of safety reports. The sponsor/investigator shall also notify FDA by telephone or by facsimile transmission of any unexpected fatal or life threatening experience associated with the use of the drug as soon as possible but in no event later than 7 calendar days after the sponsor's initial receipt of the information.

### 6.3 Data Safety and Monitoring Plan (DSMP)

A Data and Safety Monitoring Plan is required for all an individual protocols conducted at CTRC. All protocols conducted at CTRC are covered under the auspices of the CTRC Institutional Data Safety Monitoring Plan.

The CTRC Institutional DSMP global policies provide individual trials with:

- Institutional policies and procedures for institutional data safety and monitoring,
- An institutional guide to follow,
- Monitoring of protocol accrual by the CTRC protocol review committee,
- Review of study forms and orders by the forms committee,
- Tools for monitoring safety events,
- Independent monitoring and source data verification by the CTRC QA monitor/auditor,
- Monitoring of UPIRSO's by the director of quality assurance and DSMC,
- Determining level of risk (priority of audit level score – pals),
- Oversight by the data safety monitoring committee (DSMC), and
- Verification of protocol adherence via annual audit for all investigator initiated studies by the CTRC quality assurance division.

#### Monitoring Progress and Safety

Due to the risks associated with participation in this protocol, the CTRC DSMB #2 in conjunction with the Principal Investigator will perform assessment of adverse events, adverse event trends and treatment effects on this study. The CTRC DSMB #2 acts as an independent DSMB for IIS conducted at CTRC. The CTRC DSMB #2 will monitor data throughout the duration of a study to determine if continuation of the study is appropriate scientifically and ethically. An additional layer of review is provided by the CTRC Data Safety Monitoring Committee (DSMC) who will review DSMB quarterly reports.

Baseline events and adverse events will be captured using the CTRC Master Adverse Events Document for each patient using CTCAE V. 4.0 for the grading and attribution of adverse events. Usage of the CTRC Master Adverse Events Document centrally documents:

- The event and grades the seriousness of the event,
- If the event was a change from baseline,
- The determination of the relationship between the event and study intervention,
- If the event was part of the normal disease process, and
- What actions were taken as a result of the event.

#### Safety Definitions:

For this study, the following safety definitions will be applicable:

**Adverse Event Definition:** An adverse event (AE) is defined as any untoward or unfavorable medical occurrence in a human subject, including any abnormal sign (for example, abnormal physical exam or laboratory finding), symptom, or disease, temporally associated with the subject's participation in the [research](#), whether or not considered related to the subject's participation in the research for this study, all adverse events will be documented starting with specify here when you want to start collecting adverse event information, generally this would be with the first dose of the study drug and ending 30 days after the last dose of study drug is received.

**Serious Adverse Event Definition:** is any adverse event that:

1. Results in death;
2. Is life-threatening (places the subject at immediate risk of death from the event as it occurred);
3. Results in inpatient hospitalization or prolongation of existing hospitalization;
4. Results in a persistent or significant disability/incapacity;
5. Results in a congenital anomaly/birth defect; or
6. Based upon appropriate medical judgment may jeopardize the subject's health and may require medical or surgical intervention to prevent one of the other outcomes listed in this definition

**Unanticipated Problems Involving Risk to Subjects or Others (UPIRSO) Definition:**

Unanticipated problem involving risk to subjects or others includes any incident, experience or outcome that meets all of the following criteria:

- A. Unexpected (in terms of nature, severity, or frequency) given (a) the research procedures that are described in the protocol-related documents, such as the IRB-approved research protocol and informed consent document; and (b) the characteristics of the subject population being studied (note: the unfounded classification of a serious adverse event as "anticipated" constitutes serious non-compliance);
- B. Definitely related or probably related to participation in the research; and
- C. Suggests that the research places subjects or others at a greater risk of harm (including physical, psychological, economic, or social harm) than was previously known or recognized

#### Reporting Requirements

For this study, the Master Adverse Events Documents collected on patients for this protocol will be reviewed by the Principal Investigator on a quarterly basis to determine if a serious safety problem has emerged that result in a change or early termination of a protocol such as:

- Dose modification,
- Suspending enrollment due to safety or efficacy, or
- Termination of the study due to a significant change in risks or benefits.

## 6.4 PI Review

The PI will provide the DSMB #2 with the quarterly findings for discussion and review during their meetings.

As per the CTRC DSMP, any protocol modifications, problematic safety reports, unanticipated problems, and suspension or early termination of a trial must be reported to the DSMB #2 and all members of the research team. Furthermore, the PI of this study will promptly notify all study affiliates, the UTHSCSA IRB, the CTRC DSMC, and the FDA via a FDA Form 3500Aa written IND safety report of any adverse events that are either serious and/or unexpected. Suspension and early termination of a trial must also be reported immediately to the Director of Quality Assurance who will promptly notify the sponsor and the UTHSCSA IRB.

The PI will review the Master Adverse Events documents to determine the significance of the reported events and will provide findings using the Investigator Initiated Study Quarterly DSMC Report Form on a quarterly basis with the DSMB #2. The DSMB #2 will review the information provided by the PI and report to the CTRC DSMC on a quarterly basis, unless an emergent issue has been identified. The Investigator Initiated Study Quarterly DSMC Report Form includes information on adverse events, current dose levels, number of patients enrolled, significant toxicities per the protocol, patient status (morbidity and mortality) dose adjustments with observed response, and any interim findings. Any trend consisting of three or more of the same event will be reported to the CTRC DSMC for independent review outside of the quarterly reporting cycle, which begins three months following protocol start up. The DSMB #2 will also provide its findings to the CTRC's Regulatory Affairs Division so that it may be provided to the UTHSCSA IRB with the protocol's annual progress report. Conflict of interest is avoided by the independent reviews of the CTRC DSMB #2 and by ongoing independent review of UPIRSO trends by the Director of Quality Assurance.

All SAE and UPRISO's will be reported following CTRC, UTHSCSA institutional and FDA guidelines

UTHSCSA SAE/UPRISO REPORTING REQUIREMENTS For IIS that the PI holds the IND		
Type Event	Report to	Timeframe
All AE, SAE and UPIRSO	Regulatory Affairs and DQA	ASAP
All AE, SAE and UPIRSO	FDA on form 3500A	within 7 calendar days by telephone and 15 calendar days using the Form 3500A
SAE	PI at UTHSCSA	within 24 hours
SAE	UTHSCSA IRB	Annually
UPIRSO - all	PI at UTHSCSA	within 24 hours
UPIRSO - all	FDA	within 7 days
UPIRSO - life threatening	UTHSCSA IRB/UTHSCSA OCR	within 48 hours
UPIRSO - non-life threatening	UTHSCSA IRB/UTHSCSA OCR	within 7 days

#### **Expedited Reporting for Phase II and III Studies (including hospitalization\*)**

UNEXPECTED EVENT		EXPECTED EVENT	
GRADES 2 - 3	GRADES 4 - 5 Regardless	GRADES 1 - 3	GRADES 4 - 5 Regardless of

Attribution of Possible, Probable or Definite	of Attribution		Attribution

Expedited report within 10 working days
 
Grade 1 - Adverse Event Expedited Reporting NOT required.)
	
Report by phone to IDB within 24 hrs. Expedited report to follow within 10 working days.
 
This includes all deaths within 30 days of the last dose of treatment with an investigational agent regardless of attribution.
 
Any late death attributed to the agent (possible, probable, or definite) should be reported within 10 working days.
	
Adverse Event Expedited Reporting NOT required.
	
Expedited report, including Grade 5 Aplasia in leukemia patients, within 10 working days.
 
This includes all deaths within 30 days of the last dose of treatment with an investigational agent regardless of attribution.
 
Any late death attributed to the agent (possible, probable, or definite) should be reported within 10 working days.
 
Grade 4 Myelosuppression or other Grade 4 events that do not require expedited reporting will be specified in the protocol.

\* For Hospitalization Only — Any medical event equivalent to CTC Grade 3, 4, 5 which precipitated hospitalization (or prolongation of existing hospitalization) must be reported regardless of requirements for Phase of study, expected or unexpected and attribution.

Expedited reporting may not be appropriate for specific expected adverse events for certain later Phase II and Phase III protocols. In those situations the adverse events that will not have expedited reporting must be specified in the text of the approved protocol. An expected Grade 3 event that is definitely related to the investigational agent is only to be reported if the patient is hospitalized using the generic reporting criteria. For instance, in a trial of an investigational agent where Grade 3 diarrhea requiring hospitalization is expected, only diarrhea requiring ICU care (Grade 4) might be designated for expedited reporting.

Serious adverse events on NCI sponsored trials utilizing a commercially available agent (with no IND's involved) will additionally be reported via the FDA's Medwatch program.

#### Assuring Compliance with Protocol and Data Accuracy

As with all studies conducted at CTRC, the PI has ultimate responsibility for ensuring protocol compliance, data accuracy/integrity and responding to recommendations that emanate from monitoring activities. Protocol compliance, data accuracy and reporting of events is further ensured by an annual audit conducted by the Data Safety Officer, whose audit report is shared with the PI, the research team, and will be reviewed by the CTRC DSMC.

#### CTRC DSMB Membership

The CTRC has two DSMB's with a primary set of members specific to the histology of the study consisting of UTHSCSA faculty and staff. This Protocol will utilize DSMB#2 for Solid Tumor Studies.

#### CTRC DSMB Charter and Responsibilities

The CTRC DSMB will provide information on the membership composition, including qualifications and experience to both the UTHSCSA IRB and CTRC PRC for review. The CTRC DSMB for this study will act as an independent advisory board to the PI and will report its findings and recommendations to the PI, the UTHSCSA IRB and the CTRC DSMC. CTRC DSMB reports will utilize the Investigator Initiated Study Quarterly DSMC Report Form and meetings will occur on a quarterly basis to review any updates from the prior meeting.

Once the protocol is activated, if not already established elsewhere in the protocol the CTRC DSMB will establish and provide:

- Procedures for maintaining confidentiality;
- Statistical procedures including monitoring guidelines, which will be used to monitor the identified primary, secondary, and safety outcome variables;
- Consider factors external to the study when relevant information becomes available, such as scientific or therapeutic developments that may have an impact on the safety of the participants or the ethics of the study;

- Plans for changing frequency of interim analysis as well as procedures for recommending protocol changes;
- Recommendation of dose escalation, MTD recommendation of early termination based on efficacy results;
- Recommendation of termination due to unfavorable benefit-to-risk or inability to answer study questions;
- Recommendation of continuation of ongoing studies;
- Recommend modification of sample sizes based on ongoing assessment of event rates; and
- Review of final results and publications.

## 7. MANAGEMENT OF CETUXIMAB ADVERSE REACTIONS AND DOSE MODIFICATIONS

All toxicities will be graded according to NCI **Common Toxicity Criteria AE version 4.0** ([http://ctep.cancer.gov/protocolDevelopment/electronic\\_applications/ctc.htm](http://ctep.cancer.gov/protocolDevelopment/electronic_applications/ctc.htm)).

### 7.1 Cetuximab Dose Modifications

Cetuximab will be held or its dose reduced to dose level -1 or -2 (see below) for the following toxicities (see sections 7.4 and 7.5).

Cetuximab will NOT be held or reduced for hematologic toxicities.

Dose levels for cetuximab are as follows:

**Table 3: Cetuximab Dose Levels**

	Weekly Cetuximab dose
Starting dose	250 mg/m 
Dose Level -1	200 mg/m 
Dose Level -2	150 mg/m 

There will be no dose level reductions below a weekly dose of 150 mg/m^2.

### 7.2 Management of Infusion Reactions

Severe infusion reactions require the immediate interruption of cetuximab therapy and permanent discontinuation from further treatment. Appropriate medical therapy including epinephrine, corticosteroids, intravenous antihistamines, bronchodilators, and oxygen should be available for use in the treatment of such reactions. Patients should be carefully observed until the complete resolution of all signs and symptoms.

In clinical trials, mild to moderate infusion reactions were managed by slowing the infusion rate of cetuximab and by continued use of antihistamine pre-medications (e.g., diphenhydramine hydrochloride [Benadryl]) in subsequent doses. If the patient experiences a mild or moderate (Grade 1 or 2) infusion reaction, the infusion rate should be permanently reduced by 50%. For

grade 1 or 2 reactions manifesting only as delayed drug fever, see below.

Cetuximab should be immediately and permanently discontinued in patients who experience severe (Grade 3 or 4) infusion reactions.

### 7.3 Treatment of Isolated Drug Fever

In event of isolated drug fever, the investigator must use clinical judgment to determine if the fever is related to the study drug or to an infectious etiology.

If a patient experiences isolated drug fever, for the next dose, pre-treat with acetaminophen or non-steroidal anti-inflammatory agent (investigator discretion), repeat antipyretic dose 6 and 12 hours after cetuximab infusion. The infusion rate will remain unchanged for future doses.

If a patient experiences recurrent isolated drug fever following premedication and post-dosing with an appropriate antipyretic, the infusion rate for subsequent dosing should be 50% of previous rate. If fever recurs following infusion rate change, the investigator should assess the patient's level of discomfort with the event and use clinical judgment to determine if the patient should receive further cetuximab.

### 7.4 Management of Pulmonary Toxicity

In the event of acute onset (grade  $\geq 2$ ) or worsening pulmonary symptoms which are not thought to be related to underlying cancer, cetuximab therapy should be interrupted and a prompt investigation of these symptoms should occur. If ILD is confirmed, cetuximab should be discontinued and the patient should be treated appropriately.

### 7.5 Management of Dermatologic Toxicity

Patients developing dermatologic toxicities while receiving cetuximab should be monitored for the development of inflammatory or infectious sequelae, and appropriate treatment of these symptoms initiated. Dose modifications of any future cetuximab infusions should be instituted in case of severe (grade 3) acneiform rash. Treatment with topical and/or oral antibiotics should be considered; topical corticosteroids are not recommended.

If a patient experiences severe acneiform rash, cetuximab treatment adjustments should be made according to the following table. In patients with mild and moderate skin toxicity, treatment should continue without dose modification.

**Table 4 Cetuximab Dose Modification Guidelines**

Grade 3 Acneform Rash	Cetuximab	Outcome	Cetuximab Dose Modification
1st occurrence	Delay infusion 1 to 2 weeks	Improvement	Continue at 250 mg/m 
		No Improvement	Discontinue cetuximab
2nd occurrence	Delay infusion 1 to 2 weeks	Improvement	Reduce dose to 200 mg/m 
		No Improvement	Discontinue cetuximab
3rd occurrence	Delay infusion 1 to 2 weeks	Improvement	Reduce dose to 150 mg/m 
		No Improvement	Discontinue cetuximab
4th occurrence	Discontinue cetuximab		

### 7.6 In-Field Toxicities During Radiation: Radiation Mucositis/Dysphagia/Dermatitis

No cetuximab dose adjustments for grade 3 or less radiation mucositis, dysphagia, dermatitis.

Grade 4 radiation mucositis/dysphagia or dermatitis that develops at any time will require permanent dose reduction of cetuximab by one dose level on all subsequent cycles. If radiation is given in the setting of grade 4 radiation mucositis/dysphagia/dermatitis, cetuximab will be administered with a dose reduction by one dose level.

Delays in radiation as strongly discourages. Short delays may be required for the management of grade 3 /4 toxicities. If RT is held because of in-field toxicities, hold cetuximab until RT is resumed.

EGFR AS will be held for grade 3 or 4 in-field toxicities (see section 5.2.3).

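### Section 7.6 and Table 4 give different cetuximab doses when grade 4 in-field toxicity comes before the first grade 3 rash, and no rule says which prevails

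*Combined protocol and SAP*

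**What the plan says.** Five places in section 7 of the protocol bear on this. Quotes from Tables 3 and 4 lose the superscript in mg/m².

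- **Section 7.6** leaves cetuximab unchanged for in-field toxicity up to grade 3. Grade 4 radiation mucositis, dysphagia or dermatitis, whenever it occurs, "will require permanent dose reduction of cetuximab by one dose level on all subsequent cycles". The instruction is relative (one level) and permanent.
- **Table 3** defines the levels: 250 mg/m² weekly at the start, 200 at level -1 and 150 at level -2. It adds: "There will be no dose level reductions below a weekly dose of 150 mg/m".
- **Section 7.5** says that after severe acneiform rash "cetuximab treatment adjustments should be made according to the following table". It makes no exception for a patient whose dose has already been reduced.
- **Table 4** states absolute doses by occurrence of grade 3 rash, after a delay of one to two weeks and improvement: "Continue at 250 mg/m" at the first, "Reduce dose to 200 mg/m" at the second and "Reduce dose to 150 mg/m" at the third. Without improvement, or at a fourth occurrence, cetuximab stops.
- **Section 7.1** introduces the modifications and cross-refers to sections 7.4 and 7.5 only. Section 7.7 refers in-field toxicity to section 7.6, but gives no order of precedence.

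**The concern.** The two rules are written in different terms. Section 7.6 moves the patient down from wherever the patient is and makes the move permanent. Table 4 names a dose fixed by the rash count, and its first row makes sense only for a patient still on 250 mg/m². Each rule works alone. The documents do not say how they combine.

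What is at stake is patient safety and consistent treatment. Two sites reading different pages could give the same patient different doses, and one of those doses would reverse, after a grade 4 event, a reduction that the protocol calls permanent.

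**Working it through.** The documents state no figure to reproduce. The check is to follow patients through the rules as written.

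**Inputs.** Levels 250, 200 and 150 mg/m² (Table 3). One level down, permanently, after a grade 4 in-field event (section 7.6). 250, 200 and 150 mg/m² after the first, second and third improved grade 3 rash (Table 4).

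**Method.** Let G be one grade 4 in-field event and R an improved grade 3 rash. Take every order of one G with one, two or three R. Read Table 4 literally and hold the section 7.6 reduction as permanent.

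| Order | Result |
|---|---|
| G-R | First rash: 200 (7.6) against 250 (Table 4) |
| R-G | No conflict |
| G-R-R | First rash: 200 against 250. If 200 is kept, the second rash reduces to 200, the dose in force |
| R-G-R | Second rash reduces to 200, the dose in force |
| R-R-G | No conflict |
| G-R-R-R | As G-R-R. The third rash then reduces to 150 |
| R-G-R-R | Second rash reduces to 200, the dose in force |
| R-R-G-R | Third rash reduces to 150, the dose in force |
| R-R-R-G | 7.6 requires one level below 150. Table 3 has none and forbids it |

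Of the nine orders, three give two different doses (all with G first), three give only a reduction to the current dose, one meets the floor, and two are clean: 3 + 3 + 1 + 2 = 9. These counts show where the rules fail. They are not probabilities.

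**Size of the numeric conflict.** 250 / 200 = 1.25, so the Table 4 dose is 25% above the section 7.6 dose at each infusion.

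**How many patients.** Table 2 gives these grade 3/4 rates on radiation plus cetuximab: mucositis 56%, dysphagia 26%, radiation dermatitis 23%, acneform rash 17%. Only grade 4 triggers section 7.6, and its share is not reported. The grade 4 rates could therefore lie anywhere from 0 to 56%, 0 to 26% and 0 to 23%. The order of events is not reported either. Assuming the Table 2 rash rate applied to all 42 planned patients, 0.17 × 42 = 7.1 would be expected to have a grade 3/4 rash. The expected number affected then lies between 0 and about 7, and the upper end requires every one of those patients to have had an earlier grade 4 in-field event.

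**The case against.** The best defence is that Table 4 tells the patient to continue, not to increase or resume. Continuing at 250 mg/m² presupposes a patient who is receiving 250. On that reading the table is silent about patients already reduced, and the word permanent in section 7.6 governs. This is reasonable, and it means that the protocol does not expressly order a re-escalation. But the table prints a number, section 7.5 applies it to every severe rash, and nothing limits it to unreduced patients. A site has to infer the dose.

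On the floor, section 7.8 allows removal for unacceptable adverse events or on the investigator's judgment. Those are general provisions and do not settle what follows when a required reduction is unavailable. The path is also remote. Section 5 implies about eight maintenance infusions (one before radiation and about seven during it), and reaching 150 mg/m² through rash alone takes three occurrences, each with a delay of one to two weeks.

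Four stronger readings are tempting, and the documents do not support them:

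- **Every patient with both toxicities has two contradictory doses.** The numeric conflict needs the in-field event first.
- **A reduction to the current dose deprives the patient of a 50 mg/m² step.** That assumes that reductions from different causes accumulate, which no section says. At 200 mg/m² both rules are met.
- **Section 7.1 is wrong to cite section 7.4.** Section 7.1 covers holding as well as reducing, and section 7.4 interrupts cetuximab. Only the absence of section 7.6 is a gap, and section 7.7 partly covers it.
- **The conflict distorts the toxicity comparison.** The section 11.4 stopping rule concerns grade 3/4 mucositis and radiation dermatitis. A patient whose grade 4 mucositis or dermatitis triggers section 7.6 has already reached that grade for that toxicity before the doses diverge, and rash is not in the rule. No such harm is shown.

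**Conclusion.** The inconsistency is real and can be seen from the text alone. When a grade 4 in-field event at the starting dose precedes the first grade 3 rash and the rash improves, the protocol supports both 200 and 250 mg/m², and no section decides between them. This rests on reading the printed figure in Table 4 as the instruction.

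The other two consequences are lesser. The reduction to a dose already in force is an unclear instruction, not a contradiction. The collision with the 150 mg/m² floor is a rule that cannot be carried out, on an unlikely path.

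The number of patients affected cannot be stated and may be small or zero. Table 2 should not be read as giving the frequency: it pools grades 3 and 4, and its acneform rash category also includes dry skin and exfoliative dermatitis. Sample size, power and the primary analysis are unaffected. The point should be corrected because it concerns dosing after a grade 4 event and costs little to resolve.

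**What to change.** Reconcile section 7.1, Table 3, Table 4 and section 7.6 so that one scheme states:

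1. how rash and in-field modifications combine for a patient whose dose is already reduced, including which instruction prevails and whether reductions from different causes accumulate;
2. whether a reduction, once made, can be reversed;
3. what applies when a further reduction is required at the lowest level in Table 3.

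Add section 7.6 to the cross-reference in section 7.1. The choice of rule is a clinical decision for the sponsor, and this review takes no position on it. The cost is protocol wording only, with no change to sample size or analysis.
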